Persons affected by certain health conditions, including Alzheimer's disease, vestibular loss, stroke, and traumatic brain injury, as well as older adults and even some otherwise healthy individuals experience disorientation and disequilibrium. **One common type of dizziness reported across these populations is visually-induced dizziness**, which is triggered by visual stimuli such as busy patterns or moving scenes. The cause of visually-induced dizziness is believed to be **visual dependence**, a perceptual style that may be either developmental or acquired. Studying persons with this specific type of dizziness provides us unique opportunities to pursue our **long-term goals** to advance understanding of normal postural orientation and equilibrium, as well as the association between dizziness and falls.

The current standard of care for persons with visually-induced dizziness is optokinetic stimulation (repeated exposure to complex patterns and moving images). Though initial efficacy trials of this intervention were positive, results from subsequent effectiveness trials are less clear. This modality has also proven to be difficult to implement in practice due to a lack of clarity regarding treatment parameters, optimal delivery methodologies, and who will most likely benefit. As a result, use of optokinetic stimulation often results in exacerbation of symptoms and/or early withdrawal from treatment. Herein, **we introduce a promising intervention** based in part on sensory re-weighting theory and findings from preliminary work in primate and human models of bilateral vestibular ablation.

Our **central hypothesis** for this study is that intensive sensory re-weighting training will result in reduced visual dependence in healthy persons and those with visually-induced dizziness. In order to achieve this outcome, we developed these **specific aims** in the context of a phase I efficacy trial.

1. Assess the accuracy, sensitivity, and specificity of VR-based robotic verticality assessments. We will calculate the accuracy, sensitivity, and specificity of each verticality perception measure conducted while standing upright or tilted leftward or rightward in the frontal plane.

2. Determine the potential diagnostic value of IP, a postural equilibrium measure.

The IP curves of healthy persons and symptomatic persons will be significantly different (Hypothesis A).

3. Demonstrate the effects a novel sensory re-weighting intervention.

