With these data in mind, we developed an alternative intervention. We constructed a theoretical framework based on prior work that demonstrates a) there is an association between impaired verticality perception and falls(31), b) Subjective Visual Vertical is modifiable in health(32) and disease(22,33,34), c) sensory re-weighting training that upregulates somatosensory cues for postural orientation resulted in decreased dizziness and improved balance in a case of complete bilateral vestibular loss(35) and reduced visual dependence in monkeys with bilateral vestibular ablation[[name], et al., unpublished data], d) and rehabilitation of orientation in a case of stroke is task-specific(36). We now propose a new method to address the effects of impaired verticality perception on postural orientation and postural equilibrium which we believe will prove to be safer and more effective than optokinetic stimulation and that has broad applicability in balance rehabilitation.

Objectives:

We developed new methods to assess verticality perception and postural equilibrium, as well as a new method for training orientation and balance. The **specific aims** for this trial are as follows:

1. Assess the accuracy, sensitivity, and specificity of VR-based robotic verticality assessments. We will calculate the accuracy, sensitivity, and specificity of each verticality perception measure conducted while standing upright or tilted leftward or rightward in the frontal plane.

2. Determine the potential diagnostic value of IP, a postural equilibrium measure.

The IP curves of healthy persons and symptomatic persons will be significantly different (Hypothesis A).

3. Demonstrate the effects a novel sensory re-weighting intervention.

The intervention will result in reduced symptoms (Hypothesis B) and improved verticality perception (Hypothesis C). Also, changes in balance control will be detected by pre-post comparisons of the IP curves measured during visual-vestibular conflict (Hypothesis D).

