Trial Design: The study will be conducted in three phases. The first phase is for baseline testing. The second phase is when treatment occurs. The third phase is for follow up testing. Participants will be tested twice during the baseline and follow up phases. Six treatment sessions will occur during the treatment phase. Healthy adults (Group 1, n=15) and adults with self-reported visually-induced dizziness (Group 2, n=15) will undergo the same tests and will receive the same intervention.

METHODS: PARTICIPANTS, INTERVENTIONS, AND OUTCOMES

Study Setting:

This trial will be conducted at the University of Wisconsin-Madison, a level 1 research institution. Study visits will occur at the Neuromuscular Coordination Laboratory, [name], Director.

Eligibility:

Healthy Participants:

Inclusion Criteria: Participants must 1) be adults between the ages of 18 and 79 years old, 2) have normal self-reported cognitive function, 3) speak English fluently, 4) weigh less than 225 pounds and be less than 6'4", 5) be able to support their body weight in an upright posture for 15 minutes at a time, and 6) be able to follow the guidelines regarding permitted and prohibited additional treatments outlined in this protocol.

Exclusion Criteria: Participants must not 1) be pregnant or planning to become pregnant while in "on study" status, 2) have best-corrected visual acuity > 20/70, 3) have a self-reported, uncompensated, binocular vision abnormality, such as strabismus, amblyopia, or diplopia, 4) have peripheral neuropathy, and/or 5) have a self-reported history of frequent syncope (>1/month).

Participants with Visually-induced Dizziness:

Inclusion Criteria: Participants must 1) be adults between the ages of 18 and 79 years old, 2) have self-reported symptoms of visually-induced dizziness, 3) have normal self-reported cognitive function, 4) speak English fluently, 5) weigh less than 225 pounds and be less than 6'4", 6) be able to support their body weight in an upright posture for 15 minutes at a time, and 7) be able to follow the guidelines regarding permitted and prohibited additional treatments outlined in this protocol.

[figure not shown]

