Study Management: The ICTR OnCore platform will be used for overall study management. In addition, ICTR REDCap will be used to collect patient-reported outcome measures through the use of surveys, as well as performance-based outcomes through the use of standardized forms. The ICTR REDCap and ICTR OnCore systems are password protected and user's roles are defined to allow appropriate access. [name] had completed training in ICTR OnCore for protocol, financial, and study coordinators, as well as the requisite training for ICTR REDCap. Fields are programmed to ensure the validity of the data.

Statistical Methods:

Data Analysis: Standard demographic data will be collected. Age, gender, height, weight, and body mass index will be summarized with descriptive statistics. Inferential analyses are expected to be hypotheses generating. Our a-priori alpha level for all analyses is 0.05.

All data collected will be entered in a custom-built project in the UW-Madison ICTR REDCap database so that it can be securely transferred to the study biostatistician (ICTR BERD). All analyses will be conducted using "R" for statistical computing version 3.5 or higher. The study biostatistician (ICTR BERD) will provide an independent review of the data analysis.

The specific aims for this trial and related analyses are as follows:

Aim 1 Analyses: The overall scores for each verticality perception test will be analyzed for sensitivity and specificity, positive and negative predicative values, likelihood ratio, and the area under the ROC curve (AUC) for correctly identifying self-reported visually-induced dizziness(44).

Aim 2 Analysis: Euclidian distance analyses(45) will be used to compare IP curves of healthy and symptomatic persons to determine if these curves have diagnostic value for visually-induced dizziness.

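### Aim 2 bases diagnostic value for the IP curves on a significant group difference alone and, unlike Aim 1, plans no measure of how well individuals are classified

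*Combined protocol and SAP*

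**What the plan says.** Specific Aims and Objectives both state Aim 2 as: "Determine the potential diagnostic value of IP, a postural equilibrium measure". The one hypothesis under it, Hypothesis A, is: "The IP curves of healthy persons and symptomatic persons will be significantly different".

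Statistical Methods gives the Aim 2 analysis in a single sentence. Euclidean distance analyses compare the two groups' IP curves "to determine if these curves have diagnostic value for visually-induced dizziness". It names no test statistic, per-person score, cut-off or accuracy measure. The Multisensory Balance Examination section makes the IP curves themselves the measurement variables and defines no single summary of a curve.

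The sentence just before it, for Aim 1, is different in kind: "The overall scores for each verticality perception test will be analyzed for sensitivity and specificity, positive and negative predicative values, likelihood ratio", and it goes on to the area under the ROC curve. The target condition, self-reported visually-induced dizziness, is the same.

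Trial Design sets 15 participants per group, and Sample Size says withdrawals will be replaced. On error rates, Statistical Methods says "Our a-priori alpha level for all analyses is 0.05", without stating one- or two-sided testing, and describes inferential analyses as hypothesis generating.

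**The concern.** Whether two groups differ and whether a measure can tell which group a person belongs to are separate questions. A p-value depends on the number of participants; the overlap between the groups does not. With enough people, a small shift between heavily overlapping groups becomes significant while the measure stays poor at classifying anyone.

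The protocol itself judges existing tests at the level of the patient. Background and Rationale calls two established tests inadequate because, in one study of adults with this condition, 50% of patients were abnormal on one and just 15% were outside the normal range on the other. A significant group difference in IP curves cannot show whether IP does better by that standard.

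At stake is the Aim 2 conclusion. Followed as written, the plan could support a statement about diagnostic value from Hypothesis A alone, with nothing reported on how many people the measure would place correctly.

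**Working it through.** **The plan's own figure.** The plan gives no accuracy figure for IP to reproduce. The 15 per group is read from a cited table of pilot trial sizes (standardized difference 0.3 to 0.7, main trial at 90% power), so it cannot be rebuilt from the documents. Nothing below depends on it being a powered number.

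**Inputs from the documents.** n = 15 per group (Trial Design); alpha = 0.05 (Statistical Methods).

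**Assumptions that are not in the documents.** One IP score per person, normally distributed with the same SD in both groups; a two-sided t-test; a cut-off midway between the group means, which is the best cut-off under this model with equal groups.

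**Step 1. Smallest significant difference.** d = t(0.975, 28 df) × √(2/15) = 2.048 × 0.365 = 0.748.

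**Step 2. What that d means for individuals.**
- AUC = Φ(d/√2) = Φ(0.529) = 0.70
- Correct classification = Φ(d/2) = Φ(0.374) = 64.6%
- Youden index = 2 × 0.646 − 1 = 0.29

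**Step 3. Uncertainty of that AUC.** Hanley-McNeil with A = 0.7016, B = A/(2 − A) = 0.540 and C = 2A²/(1 + A) = 0.579:
- SE = √{[A(1 − A) + 14(B − A²) + 14(C − A²)]/225} = 0.096
- 95% CI = 0.70 ± 1.96 × 0.096 = 0.51 to 0.89

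**Step 4. Sensitivity to the assumptions.**
- Normal quantile instead of t: d = 0.716, 64.0% correct.
- One-sided t-test: d = 0.621, 62.2% correct.
- Curve treated as p features, with a just-significant Hotelling test. D² = F(0.95; p, 29 − p) × 28p/(29 − p) × 2/15. Bias-corrected D² = D² × (27 − p)/28 − 2p/15. Accuracy = Φ(D/2):

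| p | D | Apparent accuracy | Bias-corrected D | Bias-corrected accuracy |
|---|---|---|---|---|
| 1 | 0.748 | 64.6% | 0.621 | 62.2% |
| 2 | 0.963 | 68.5% | 0.749 | 64.6% |
| 3 | 1.132 | 71.4% | 0.836 | 66.2% |
| 5 | 1.428 | 76.2% | 0.967 | 68.6% |
| 8 | 1.855 | 82.3% | 1.127 | 71.3% |

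Apparent accuracy rises with p because the same 30 people both fit and test the rule. After bias correction the range is about 62% to 71%.

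**Step 5. How far significance lies from good classification.** For 80% correct, Φ(d/2) = 0.80 needs d = 2 × 0.842 = 1.68. At 15 v 15 that gives t = 1.68/0.365 = 4.6 and p of about 0.0001. Under this model the 0.05 threshold is crossed well before that level of discrimination is reached.

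**The case against.** The strongest defence is that this is a preliminary study. The aim speaks of potential diagnostic value, inferential analyses are labelled hypothesis generating, and the Dissemination Policy expects the data to drive further development of the tests. For a new measure, asking first whether affected and healthy people differ is a reasonable step. This stands, and it limits the consequence. It does not remove the mismatch: Aim 1 sits under the same label and still reports accuracy, and the Aim 2 analysis sentence drops the word potential.

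A second defence is that an AUC at 15 v 15 will be imprecise. That is true, and showing the interval is a reason to report it.

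Some stronger readings are tempting, and the documents do not support them:

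- A reader might infer that the planned analysis can classify only 65% of people. The planned comparison is a distance analysis of whole curves with no stated statistic, so 65% is an illustration at the significance threshold. It is not a property of that analysis or a ceiling for IP.
- A reader might infer that a group difference carries no information about classification. The working itself converts one into the other under a model. What holds is that significance alone does not establish adequate classification.
- A reader might infer that only group averages will be compared. The method is too briefly described to say so; the text supports only that no individual-level measure is stated.
- A reader might infer that a planned comparison of IP with the verticality tests is undermined. No such comparison appears in the aims or Statistical Methods.

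**Conclusion.** The point holds as a gap between the Aim 2 question and its analysis: a significant difference is the only criterion stated, and no accuracy measure is planned for IP. That rests on the text and needs no calculation.

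The size is illustrative. It assumes one normal score per person (or a small set of normal features), equal spread and a result exactly at the significance threshold. On those terms a positive Hypothesis A could go with an AUC of about 0.70 and some 62% to 71% of people correctly classified. A result well beyond the threshold would mean better classification, by an amount the plan would leave unreported.

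The change is worth making before the IP data are analysed. The hypothesis-generating status keeps the point moderate, and it does not affect the pre-post analyses of Aim 3.

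**What to change.** Keep the Euclidean distance comparison as the test of Hypothesis A. Then add the following to the Aim 2 analysis:

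1. Before the IP data are analysed, the investigators prespecify one baseline IP score per participant, either a summary of the curve or a distance from a reference curve. They state which balance condition and which of the two pre-tests it uses.
2. Report the AUC of that score for self-reported visually-induced dizziness, with a 95% CI, as for Aim 1. If the score is derived from the group data, cross-validate it.
3. Base any statement about potential diagnostic value on the AUC and its interval, described as hypothesis generating. Without the AUC, word the Aim 2 conclusion as a group difference only.

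The cost is one derived variable and one further analysis of data already scheduled for collection, with no extra visits or participants. The choices are not trivial, because the documents give no frequency band, summary or cut-off for IP. A single score also describes the curve incompletely. Precision will be poor: the interval around an AUC of 0.70 runs from about 0.51 to 0.89, and a sensitivity of 12/15 (80%) would have an exact 95% CI of 52% to 96%.

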Gait Speed: A 10-meter walk test will be conducted with eyes open and eyes closed in accordance with previously published methodology(39). Participants will be allowed one practice trial for each condition.

Participation Timeline:

Including a telephone screening, there are 9 study contacts over 6 weeks. Questionnaires, as well as tests of verticality perception, balance, and gait are to be collected in weeks 1, 2, 4, and 5 (see Table 2, page 19). The intervention will be conducted 2 times during each twice-weekly visit in weeks 2, 3, and 4. This research is being conducted in the UW-Madison Neuromuscular Coordination Laboratory.

In order to substantially reduce the time each participant is required to be in the lab and increase accuracy of data collection, patient-reported outcomes will be administered via ICTR REDCap. Measures will be collected up to 24 hours before visits 1 and 2, as well as up to 24 hours after visit 3, and up to 24 hours before visit 4 in order to ensure patient-reported and performance-based outcomes are administered at the same time points. Pre-testing with the performance-based outcomes described in this protocol will occur at visit 1 and immediately prior to training during visit 2. Post-testing with the performance-based outcomes will take place immediately after training during visit 7, as well as during visit 8. The intervention will be provided during visits 2 and 3. The data collected at each time point is shown in Table 3.

Participants will be in "on treatment" status during weeks 2-4. "Off study" status coincides with the completion of post-testing.

	Week 0	Week 1	Week 2	Week 3	Week 4	Week 5
Activity						
Screening	Before enrolled					
Outcomes		Baseline 1	Baseline 2		Post-test 1	Post-test 2
Training			2x/week	2x/week	2x/week	

Table 2: Participation Timeline:

Table 3: Data Collected at Each Assessment Timepoint

Measure	Pre-test 1	Pre-test 2	Post-test 1	Post-test 2
VVAS	Х	Х	Х	Х
VRD-25	Х	Х	Х	Х
ABCS	Х	Х	Х	Х
DHI	Х	Х	Х	Х
VAPM	Х			Х
VRBQ	X			X
SVV	Х	Х	Х	Х

RFT	Х	Х	Х	Х
RDT	Х	Х	Х	Х
MBE	Х	Х	Х	Х
FGA	Х			Х
Gait Speed	Х			Х

Sample Size:

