We based sample size on Whitehead et al,(40) (pg. 1071, Table 8) who recommends a sample size of 15 subjects per group for a efficacy trial when the main trial is expected to generate a medium-sized standardized mean difference of 0.3 to 0.7 at 90% power. Subjects who withdraw for any reason will be replaced. All analyses will be conducted once the last participant completes participation.

Recruitment:

Recruitment (Background): Motion sickness is an extremely common phenomenon, particularly in persons with vestibular disorders. Data regarding the prevalence of visually-induced motion sickness is limited. The prevalence of motion sickness varies based on factors such as age, gender, nationality, occupation, etc (41). One-third of adults in the general population report they experience such symptoms(42). Similarly, Strupp, et al.(43) found nearly one-third of persons presenting to a tertiary center for vertigo reported a history of motion sickness. They concluded that motion sickness is a relevant comorbidity for persons with vestibular disorders. Thus, we anticipate being able to quickly recruit the suggested number of participants from UW Health, UW-Madison, and the surrounding community within 6 months of opening.

Indirect recruitment by posting advertisements (See attached file: HIRES Efficacy Trial Study Ad V1): Advertisements will be posted in the waiting rooms of the University of Wisconsin Hospital and Clinics (UWHC), Ear, Nose, and Throat (ENT) Clinic, clinics affiliated with the UWHC Department of Orthopedics and Rehabilitation (UW Health at the American Center, Yahara Clinic, Clinical Sciences Center, Research Park Spine Clinic and Sports Rehabilitation Clinic, and Middleton Rehabilitation Clinic), and on bulletin boards within the University of Wisconsin-Madison (UW-Madison) Department of Kinesiology, Occupational Therapy Program, and Physical Therapy Program. Permission to post advertisements will be obtained from [name], Clinical Manager of Otolaryngology; [name], Director, Department of Orthopedics and Rehabilitation, [name], Chair, Department of Kinesiology; and [name], Director, Physical Therapy Program. [name]

will ensure that postings follow applicable policy and are removed after enrollment is closed.

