Aim 3 Analyses: Standardized mean difference will be used to assess if the intervention resulted in reduced symptoms based on pre-post comparisons of the Visual Vertigo Analogue Scale total score. Standardized mean difference will also be used to assess if the intervention resulted in improved verticality perception based on an effect size of 0.5 for pre-post comparisons of the average scores for the Rod and Disk Test, our primary outcome. Euclidian distance analyses will be used to assess for changes in balance control based on pre-post comparisons of the IP curves measured during visual-vestibular conflict. We will determine what, if any, immediate and short-term treatment effects resulted from the training by analyzing the data collected immediately pre- and immediately post-training. We will assess for short-term retention of any treatment effects by comparing outcomes measures data collected immediately following training and one week later.

Missing Data: We will conduct sensitivity analysis of missing data and follow the intention to treat principle.

We also plan to assess for relationships between our various outcome measures. These analyses will involve determining correlations between each of the patient-reported outcomes and between the patient-reported and performance-based outcomes. These secondary analyses will also be considered hypothesis generating and will be conducted at an unadjusted significance level of 0.05.

Feasibility and Contingency Plans:

Our ongoing research at UW Health and UW Madison has enrolled more than the necessary numbers of subjects for this study. In the event of sluggish enrollment, recruitment will be expanded to additional clinics. In anticipation that some participants may not tolerate testing well, specific guidance regarding modifying the intervention will be provided. Should any system fail to collect data, the visit will be rescheduled, or an additional visit will be added if necessary, in keeping with the study timelines

outlined in this protocol. No additional reimbursement to participants related to rescheduling or adding a research visit. Institutional support will be sought immediately if any key study staff leave.

METHODS: MONITORING

Data Monitoring:

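### Short-term retention is defined only as Post-test 1 versus Post-test 2, which measures decay; no baseline versus Post-test 2 contrast is named to show the gain still present at one week

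*Combined protocol and SAP*

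**What the plan says.** The Participation Timeline (Table 2) sets four assessments: "Baseline 1 Baseline 2 Post-test 1 Post-test 2". Table 3 shows that RDT, SVV, RFT, MBE, VVAS, VRD-25, DHI and ABCS are collected at all four. VAPM, VRBQ, FGA and gait speed are collected only at Pre-test 1 and Post-test 2.

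Aim 3 Analyses names two time contrasts:

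- Treatment effect: the plan will look for "immediate and short-term treatment effects resulted from the training by analyzing the data collected immediately pre- and immediately post-training". This is Pre-test 2 against Post-test 1.
- Retention: "We will assess for short-term retention of any treatment effects by comparing outcomes measures data collected immediately following training and one week later". This is Post-test 1 against Post-test 2.

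The same section judges verticality perception "based on an effect size of 0.5 for pre-post comparisons of the average scores for the Rod and Disk Test, our primary outcome". Data Analysis adds: "Our a-priori alpha level for all analyses is 0.05". No retention margin, confidence interval or decision rule is given. According to the Participation Timeline, the performance tests for Post-test 1 are done straight after that day's training at visit 7, and those for Post-test 2 at visit 8.

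**The concern.** Retention, in the ordinary sense, means that a gain over baseline is still there later. A comparison of the two post-tests contains no baseline, so it answers a different question: how much changed in the week after training ended. A small change fits a gain that was kept, and equally no gain at all. In a small sample, a change that is merely not significant also fits a gain that was lost.

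The reference point is also exposed. For the performance outcomes, Post-test 1 follows training rounds in the same device, with feedback on rod judgements, within the same visit. Same-session practice, fatigue or brief symptoms could shift it in either direction. A lasting gain could then look lost, or a loss could be hidden. Post-test 2 is the only post-training assessment free of this, yet it enters no named comparison with baseline.

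At stake is what can be said about benefit one week after a six-session programme.

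**Working it through.** **1. The plan's own figure.** The 15 per group is taken from a published pilot-trial table, which is not in the documents, so it cannot be reproduced here. The 90% power and the SMD range of 0.3 to 0.7 quoted with it (Sample Size) belong to a later main trial. The plan makes no power statement for the retention contrast.

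**2. Inputs.**

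- n = 15 per group (Trial Design).
- Alpha 0.05 (Data Analysis); two-sided is assumed.
- Effect 0.5 (Aim 3 Analyses). The standardizer is not stated; the raw-score SD is used first.
- Correlation r between Post-test 1 and Post-test 2 is not given; assumed from 0.3 to 0.9.
- SDs at the two visits are assumed equal.

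**3. Formulas, in raw-score SD units.**

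- SD of the paired difference = √(2(1 − r)).
- Paired effect size for a loss L: d_z = L / √(2(1 − r)).
- Power = P(|T| > 2.145), with T noncentral t on 14 df and noncentrality d_z × √15.
- 95% CI half-width = 2.145 × √(2(1 − r)/15).

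Example at r = 0.5 with complete loss (L = 0.5): the SD of the difference is 1.0, d_z = 0.5, the noncentrality is 0.5 × 3.873 = 1.94, and power is 0.438. The half-width is 2.145 × √(1/15) = 0.554.

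| r (assumed) | SD of difference | d_z, complete loss | Power, complete loss (0.5 SD) | Power, half lost (0.25 SD) | 95% CI half-width (SD) |
|---|---|---|---|---|---|
| 0.3 | 1.183 | 0.423 | 33% | 12% | 0.66 |
| 0.5 | 1.000 | 0.500 | 44% | 15% | 0.55 |
| 0.7 | 0.775 | 0.645 | 64% | 21% | 0.43 |
| 0.8 | 0.632 | 0.791 | 81% | 30% | 0.35 |
| 0.9 | 0.447 | 1.118 | 98% | 52% | 0.25 |

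Power of 80% against complete loss needs r of about 0.79. The half-width exceeds the 0.5 SD effect only when r is below about 0.59. If 0.5 is instead in units of the SD of change, and the Post-test 1 to Post-test 2 difference has that same SD, power is 44% and the half-width 0.55.

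**4. Could the contrast show retention positively?** Take an illustrative equivalence margin of 0.25 SD, half the effect, and suppose nothing is lost. Two one-sided tests at n = 15 would succeed in under 1% of trials for r up to 0.7, about 4% at r = 0.8 and 34% at r = 0.9.

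**5. The contrast that is not named.** Pre-test 2 to Post-test 2 equals (Post-test 1 − Pre-test 2) + (Post-test 2 − Post-test 1). For complete cases, the mean change is therefore the sum of the two named contrasts. Its CI is not: that needs their covariance, or a direct analysis of the paired difference. If a 0.5 SD gain were fully kept, the expected 95% CI for the net change, where r is now the Pre-test 2/Post-test 2 correlation, would be:

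- r = 0.5: 0.5 ± 0.55, or −0.05 to 1.05
- r = 0.7: 0.5 ± 0.43, or 0.07 to 0.93
- r = 0.9: 0.5 ± 0.25, or 0.25 to 0.75

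**The case against.** The other side has several good points.

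- **Power.** A reader might infer that 15 per group cannot separate full retention from complete loss. The documents do not support that. The answer turns on a correlation they do not give: at r of 0.8 or more, power against complete loss of 0.5 SD is 81% or higher, and pooling both groups (n = 30) gives 75% even at r = 0.5. What stands is that the contrast is weak at low to moderate r, and weak against partial loss over nearly all of the range.
- **Net benefit.** A reader might infer that the one-week net effect is never estimated. That also goes too far. The outcome descriptions define the metric as a pre-test to post-test difference without saying which post-test, and four measures exist only at Pre-test 1 and Post-test 2. Yet Aim 3 writes no analysis for those four, and where it does attach timepoints to the treatment effect, it uses the immediate post-test.
- **Decision rule.** A reader might infer that a non-significant change will be declared retention. The plan does not say so. Its stated tool for VVAS and RDT is an SMD, which is an estimate, and it looks for a treatment effect before asking whether it was retained. That reduces the risk of claiming retention of a gain that never occurred. It does not supply the missing contrast.
- **Legitimacy and status.** Post-test 1 versus Post-test 2 is a valid measure of decay, and inference is labelled hypothesis generating. Both are true. They limit the weight of the point and are reasons to keep the existing contrast.

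**Conclusion.** The point holds in a limited form. For the eight outcomes measured four times, the only named use of the one-week data is against Post-test 1. That contrast alone cannot show that a gain over baseline persists, and for performance outcomes its reference may carry a same-session effect.

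On size: power at 15 per group to detect complete loss of a 0.5 SD gain is about 33% to 64% for r of 0.3 to 0.7, rising to 81% and 98% at r of 0.8 and 0.9. For loss of half the gain it is 12% to 52% over the whole range. A non-significant change is therefore not evidence of retention. These figures rest on a two-sided 0.05 test, equal SDs and assumed correlations.

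This is an inexpensive improvement to an exploratory analysis, not a defect that undermines the trial's main conclusions.

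**What to change.** In Aim 3 Analyses:

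1. Pre-specify the Pre-test 2 to Post-test 2 change as the one-week net effect: mean change and SMD with 95% CI, by group, for the outcomes measured four times, with the corresponding Euclidean distance comparison for the IP curves.
2. Keep the Post-test 1 to Post-test 2 change, with its 95% CI, as the measure of decay.
3. State that a non-significant Post-test 1/Post-test 2 difference will not be taken as evidence of retention.

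Interpret both estimates through their intervals. Do not add a rule that retention is claimed when the net-change interval excludes zero. At equal r, that rule has the same power as the existing contrast: at r = 0.5 a fully kept 0.5 SD gain would meet it only 44% of the time. It could also count a gain that had partly gone as retained.

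The cost is a few sentences. No new visits or data are needed. The change affects what is estimated, not how precisely.
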